The statistical analysis plan was developed by [name], biostatistician expert on the trial's Steering Committee, and Lead Biostatistician at the DCC. The primary hypothesis concerns non-inferiority of shortened-duration when compared with conventional duration anticoagulation therapy. In accordance with the convention for non-inferiority trials, the primary analysis is per-protocol (PP) for the primary endpoint. Analytic populations will be defined as follows:

- a) Intent-to-treat (ITT): All randomized patients (i.e., excluding those in the parallel cohorts), analyzed according to randomization assignment.
- b) Per-protocol: All randomized patients (i.e., excluding those in the parallel cohorts) who: completed follow-up through at least the 6 month visit; received 80% and 120% of doses of anticoagulant medication based on protocol-prescribed randomized duration of anticoagulation; AND had no protocol violations in eligibility criteria.
- c) Safety: All randomized patients who have received at least 1 dose of anticoagulant post-enrollment.

The original design of the Kids-DOTT trial was based on historical observational studies which report a 10% annual rate of recurrent VTE and a 10% annual rate of clinically relevant bleeding. In the first half of the trial the risk has been much lower than the original design assumptions; that is, the observed risk is about 3% for recurrent VTE and about 1% for the bleeding endpoint. The updated Kids-DOTT statistical analysis plan describes how the bivariate decision curve will be revised when the recurrent VTE and bleeding risks differ from the pre-trial estimates. The analysis plan does not include an interim analysis because the reduced risk for the VTE and bleeding endpoints does not provide sufficient information to support an interim analysis prior to trial completion.

[figure not shown]

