It is important to recognize that no relevant placebo-controlled RCT data exist by which to understand the effect size of anticoagulant therapy, and hence to inform the statistical calculation of a non-inferiority margin in this manner. Therefore, the non-inferiority margin has been set by clinical consensus among the participating investigators and with the approval of the Steering Committee, as an absolute increase of <6% in the risk of recurrent VTE at one year for the shortened-duration arm relative to the conventional-duration arm. Statistical methods for sample size estimation have then employed this margin as the upper bound of the 95% confidence interval. Therefore, upon trial completion we will conclude non-inferiority if the upper limit of the final 95% confidence interval rules out an absolute increase in symptomatic recurrent VTE of 6% or larger. When the upper bound of the 95% confidence interval is less than 6%, the **observed absolute increase in symptomatic recurrent VTE will be <1%**. The acceptability of this non-inferiority margin on the primary efficacy endpoint is based on a simultaneous presumption of reduction in risk of clinically-

relevant bleeding (i.e. bivariate endpoint approach)—specifically, a **hypothesized absolute risk reduction in clinically-relevant bleeding of $\geq 5\%$** —as further detailed below.

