Given that duration of anticoagulation in VTE reflects a balance between efficacy (symptomatic recurrent VTE) and safety (clinically-relevant bleeding) as defined in the Primary Outcome Measures section above and given the hypothesis that bleeding will be reduced in children receiving shortened-duration anticoagulation, the statistical analysis will employ a bivariate endpoint analysis (i.e., trade-off approach). With a sample size of 285 per group in the randomized population, there is 82% power to conclude non-inferiority at an observed absolute increase in recurrent VTE of 1% (i.e., critical value of 1%, 95% CI upper bound of $<6\%$), with an observed absolute decrease in clinically significant bleeding of 5%. Accounting for an estimated rate of persistently occlusive thrombosis of 15% at 6 weeks (randomization exclusion), and an anticipated non-retention rate of 25% for the primary endpoint at 1 year follow-up, a **total randomized population of 420 participants is targeted to meet study goals of a total of 316 participants in the primary analysis population (1 year follow-up primary endpoint)**. Based on most recent randomization rates (28 June 2019) we estimate a total enrollment of 609 in the randomized and observational components of the Kids-DOTT study. The bivariate endpoint analysis statistical function for the completed trial is graphically depicted in **Figure 2**. The methods used to define the bivariate decision curve are described in the SAP. The SAP also describes how the decision curve changes when the event rate differs from the pre-trial design.

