1.2 Statistical decision criteria using the bivariate (recurrent VTE:bleeding) outcome

1.2.1 Decision criteria for ARR in recurrent VTE and bleeding endpoints

[figure not shown]
A bivariate recurrent VTE:bleeding tradeoff curve for treatment effects measured by ARR was selected to have appropriate bivariate inference at 3 reference design points (Table 1, below): point A represents an important reduction in bleeding risk with a slight increase in srVTE risk, point B represents a smaller reduction in clinically relevant bleeding risk with no effect on srVTE risk, and point C indicates a slight increase in clinically relevant bleeding risk that is offset by a significant reduction in srVTE risk. As in any trial design, such reference points are selected because they represent effects that should engender appropriate decisions and statistical inference. Specifically, if there is evidence of a highly significant reduction in clinically relevant bleeding risk for the study intervention (shortened-duration anticoagulation), then a non-inferiority conclusion can be defended even if there is a slight increase in srVTE risk (point A: -12% bleeding risk reduction [95% confidence interval: -0.169 to -0.071] and 1% recurrent VTE risk increase [95% confidence interval: -0.039 to 0.059]). However, closer to the origin (point B), non-inferiority is decided when there is no difference in symptomatic recurrent VTE risk, but a slight reduction in clinically relevant bleeding risk. Although unlikely, point C represents a significant reduction in srVTE risk that offsets a 4% increase in clinically relevant bleeding risk.

Table 1. Statistical inference at the 3 reference design points on the Kids-DOTT decision curve assuming 285 subjects per group and 10% event risk.

Hypothetical Result	VTE risk difference		Bleed risk difference	
	Observed	95% CI	Observed	95% CI
A	0.01	(-0.039, 0.059)	-0.12	(-0.169, -0.071)
B	0.00	(-0.049, 0.049)	-0.04	(-0.089, 0.009)
C	-0.05	(-0.099, -0.001)	0.04	(-0.009, 0.089)

The methods of Kittelson et al. [1,2] are used to create a smooth curve through the three reference points to define bivariate decision criteria is given in Appendix equation (1) and is plotted in Figure 1.

Figure 1. Protocol-specified bivariate decision criteria for ARR for risk of srVTE and clinically relevant bleeding (Appendix equation 1).

[figure not shown]

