As an example, using the decision curve of Appendix equation (1) the trial has 81.3% power under the hypothesis that there is no difference between short and standard duration therapy on the risk of symptomatic VTE recurrence ($\delta_V = 0$) and a 1.64 standardized reduction in the standardized mean effect on clinically relevant bleeding risk ($\delta_B = -1.64$). Assuming that the risk of srVTE is 3% and the true clinically relevant bleeding risk is 1%, then the trial has 81.3% power under the hypothesis that ARR for srVTE risk is 0 and ARR for clinically relevant bleeding risk is reduced by 1.4% (i.e., -1.64 times the standard error for bleeding, 0.0083). A reduction in the risk of srVTE and bleeding gives more power for the NI decision, as evidenced by the fact that the green lines in [Figure 2](#) are shifted to the northeast relative to the red line.

In addition to trial power, it is useful to evaluate the likely width of the 95% confidence interval upon trial completion. [Table 4](#) shows how the trial sample size affects the length for the srVTE and bleeding outcomes. As described above and illustrated [Figure 2](#), the critical value curve is determined by the size of the confidence rectangle (formed from the 95% confidence intervals for bleeding and srVTE). For example, with a total of 570 patients in the primary analysis population ([Figure 2](#) solid green line), the 95% confidence rectangle has total width of 5.6% horizontally and 3.2% vertically. If there are 316 patients in the primary analysis population, then the rectangle is 7.6% horizontally and 4.4% vertically ([Figure 2](#) dashed green line).

Table 4: Length (half-width) of 95% confidence interval as a function of sample size.

Number randomized	570	416	354	332	316	292	270
CI half-width for srVTE (3% risk)	0.028	0.033	0.036	0.037	0.038	0.039	0.041
CI half-width for bleeding (1% risk)	0.016	0.019	0.021	0.021	0.022	0.023	0.024

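### The protocol's assurance that an upper limit below 6% means an observed recurrence increase below 1% belongs to the original 10%-risk, 570-patient design and is not a property of the current one

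*Protocol*

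**What the plan says.** Protocol section IV.H (Data Analysis Plan) sets the margin "as an absolute increase of <6% in the risk of recurrent VTE at one year" for the short arm relative to the conventional arm. Non-inferiority is to be concluded at trial completion if the "upper limit of the final 95% confidence interval rules out an absolute increase in symptomatic recurrent VTE of 6% or larger". The next sentence, partly in bold, says that whenever the upper bound is below 6% the "observed absolute increase in symptomatic recurrent VTE will be <1" per cent. No event risk, sample size or interval method is attached to it. The power paragraph that follows repeats the figure for 285 per group ("critical value of 1%, 95% CI upper bound of" 6%).

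Earlier in the same section the protocol reports that "the observed risk is about 3% for recurrent VTE and about 1% for the bleeding endpoint", against a design assumption of 10% for each. It now aims for 420 randomised and 316 in the primary analysis.

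SAP section 1.2.1, Table 1, is computed "assuming 285 subjects per group and 10% event risk". Its reference point A is a "1% recurrent VTE risk increase [95% confidence interval: -0.039 to 0.059". SAP section 1.3.2, Table 4, has a row headed "CI half-width for srVTE (3% risk"), with 0.028 at 570 patients and 0.038 at 316. SAP section 2.1.3 specifies exact (melded) intervals for the final analysis and decides by whether the confidence rectangle excludes the bivariate bound. SAP section 2.1.1 calls the trial positive only if the per-protocol and ITT analyses agree.

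**The concern.** For a fixed upper limit, the largest observed difference that still passes is the margin minus the interval's half-width. The half-width depends on event risk and sample size, so a fixed ceiling of 1% can hold only for particular values of both. Risk and sample size have changed, and the decision curve was revised to match, but this sentence was not.

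The sentence tells a reader how much worse the short arm could look and still meet the 6% limit. Anyone relying on it would take an upper limit below 6% as proof that the observed excess was under 1 point, and that need not be so.

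**Working it through.** **Inputs.** Margin 0.06 and two-sided 95% interval (protocol IV.H). Standard error of the risk difference √(2p(1−p)/n), n per arm (SAP Appendix). Risks of 10% (original) and 3% (current). I assume equal arms: 285 (570 patients), 210 (420 randomised) and 158 (316 analysed).

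**1. Reproducing the plan's figure.** Ceiling = 0.06 − 1.96 × SE. At p = 0.10, n = 285:
- SE = √(2 × 0.10 × 0.90 / 285) = 0.0251
- half-width = 1.96 × 0.0251 = 0.0493
- ceiling = 0.06 − 0.0493 = 0.0107, or 1.07 points

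This agrees with Table 1 point A (observed 0.01, upper limit 0.059). The 1% is the original critical value, rounded.

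**2. Same formula at 3% risk.**

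| Per arm | SE | Half-width | Table 4 | Ceiling |
|---|---|---|---|---|
| 285 | 0.0143 | 0.0280 | 0.028 | 3.2 points |
| 158 | 0.0192 | 0.0376 | 0.038 | 2.2 points |

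**3. Exact intervals, as planned.** For x₁ events in the short arm and x₀ in the conventional arm, the melded upper limit is the 97.5% quantile of Beta(x₁+1, n−x₁) − Beta(x₀, n−x₀+1), the two taken as independent. Selected results, short v conventional:

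| Per arm | Events | Pooled risk | Observed increase | Upper limit | Below 6%? |
|---|---|---|---|---|---|
| 285 | 12 v 5 | 2.98% | +2.46 | 5.79% | yes |
| 285 | 13 v 5 | 3.16% | +2.81 | 6.22% | no |
| 210 | 8 v 4 | 2.86% | +1.90 | 5.83% | yes |
| 210 | 8 v 5 | 3.10% | +1.43 | 5.45% | yes |
| 210 | 9 v 4 | 3.10% | +2.38 | 6.44% | no |
| 158 | 6 v 5 | 3.48% | +0.63 | 5.57% | yes |
| 158 | 6 v 4 | 3.16% | +1.27 | 6.08% | no |
| 158 | 5 v 4 | 2.85% | +0.63 | 5.25% | yes |
| 158 | 5 v 3 | 2.53% | +1.27 | 5.75% | yes |
| 158 | 4 v 1 | 1.58% | +1.90 | 5.87% | yes |
| 158 | 3 v 0 | 0.95% | +1.90 | 5.45% | yes |

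At 158 per arm, every passing result with 9 or more events in total has an increase of at most 0.63 points. A total of 8 is the first, counting down, at which a passing result exceeds 1 point. Because counts are discrete, the ceiling does not move smoothly: 14 events at 210 per arm (3.33% pooled) allow only 8 v 6, +0.95.

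**4. The bivariate rule.** Solving SAP equation (3) for the recurrence difference:

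ARR_V = 0.025 + 0.0493 − 1.96·S_V + 0.003 / (ARR_B − 0.08 − 0.0493 + 1.96·S_B)

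With 3% and 1% risks and 158 per arm, 1.96·S_V = 0.0376 and 1.96·S_B = 0.0219. A bleeding difference of 0 gives 0.0366 − 0.0280 = 0.0087; a difference of −1 point gives 0.0366 − 0.0256 = 0.0111, with inputs carried unrounded. At 285 per arm the corresponding values are 0.0197 and 0.0218. The smooth curve therefore allows about 0.9 to 1.1 points at 316 patients and 2.0 to 2.2 at 570.

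**The case against.** The strongest reply is that the interval in question is the exact one, not the normal approximation behind Table 4. At the planned per-protocol size and about 3% risk, 316 patients yield about 9.5 events, and every passing result with 9 or more events shows an increase of at most 0.63 points. In that setting the statement is true. The bivariate curve at 316 also allows only about 1 point when bleeding differs by 0 to −1 point. The SAP says openly, in section 1.3.1, that lower variance enlarges the non-inferiority region. The protocol places the primary database lock in March 2021, before this document's date, so no primary decision turns on the sentence.

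Much of this stands, and it limits the size of the point. It does not rescue an unconditional statement. The ITT analysis, which must agree, breaches it near 3% risk (8 v 4 at 210 per arm), and the per-protocol analysis breaches it if recurrence is somewhat lower (5 v 3).

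Two stronger readings are tempting and unsupported. A reader might infer that at today's 3% risk the short arm could look 2 to 3 points worse at the planned size, a two-thirds relative increase on 3%. With exact intervals at 158 per arm, 8 v 5 events (+1.90 points) has an upper limit of 7.19% and fails. A reader might also infer that the statement holds only at 10% risk. That is about right for 570 patients, where the normal-approximation ceiling falls to 1% at 10.3% risk. At 316 patients it does so from about 5.4%.

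**Conclusion.** The sentence is un-updated text from the original design. It is not a calculation error: 1.07 points reproduces. As a general property of the 6% criterion it is wrong.

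The size of the gap depends on method and population. It is largest under the Table 4 normal approximation. Under the planned exact method near 3% pooled risk, it persists at 285 per arm and at 210 per arm, and disappears at 158 per arm unless pooled risk falls to about 2.5% or below. These results assume equal arms, no mid-p adjustment (the SAP mentions none) and, for ITT, all 420 randomised patients in the denominator. The margin, the sample size and the operative bivariate rule are unaffected. The consequence is for documentation and for how a result is read.

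**What to change.** Delete the <1% assurance from protocol section IV.H. Alternatively, keep it and label both it and the 1% critical value in the power paragraph as belonging to the original design (10% risk, 285 per arm).

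If a current figure is wanted, state the assumed risk, sample size and interval method. Suitable wording in substance: at about 3% pooled risk and with exact intervals, about 0.6 points at 158 per arm, 1.4 to 1.9 at 210 and 2.5 at 285, with 1.3 to 1.9 possible at 158 per arm if pooled risk is about 2.5% or lower. The 2.2 and 3.2 values should appear only if marked as Table 4 normal approximations. Add that the decision itself is made by the bivariate rule.

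The cost is one or two sentences. Nothing in conduct or analysis changes, though the stated ceiling becomes less favourable in some settings.

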As reflected in the Statistical Analysis Plan, the risk differences (absolute risk reduction, ARR) for both the primary efficacy and primary safety endpoints will be used with the curve in **Figure 2** to determine the non-inferiority decision. The decision curve in **Figure 2** (red line) is based on the original design assumption of a 10% risk for recurrent VTE and a 10% risk for clinically significant bleeding. Based on these assumptions, 570 randomized patients would be expected to produce 57 primary efficacy events and 57 primary safety events in the RCT primary analysis population. With the current risk of recurrent VTE (3%) and bleeding (1%) the decision curve is shifted toward the non-inferiority bound (**Figure 2** blue line). **Figure 2** shows the decision curve with the anticipated 316 subjects in the randomized treatment study (dashed green line). The methods for deriving these decision curves are provided in the SAP.

Figure 2: Bivariate decision criteria.

I. Data Management and Security

During the pre-NIH and NIH award period, data management and security were facilitated by CPC Research via a vendor-hosted, web-based, secure, user-restricted, password-protected, Electronic Data Capture (EDC) system, DATATRAK™. Data export and transfers to the University of Colorado-based lead biostatistician at the DCC are executed via a secure, user-restricted, password-protected server that resides behind the firewall at the University of Colorado School of Public Health. Database lock of this 'primary database' occurred in March 2021. A 'secondary' REDCap database hosted at JHACH will allow collection of continued 2-year follow-up visits and outcome events. Completion of all study visits is anticipated to occur by January 2022.

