1.3.2 Trial power

With bivariate decision criteria, the power of the trial must be evaluated using a bivariate probability distribution. [Table 2](#) shows the power for a non-inferiority decision of the bivariate design at the standardized mean treatment effects on srVTE and clinically relevant bleeding. [Table 3](#) shows the transformation of the standardized mean treatment effects into the ARR scale using different standard errors. The power from [Table 2](#) applies to the transformed effects in [Table 3](#).

Table 2: Power under the bivariate decision rule for standardized true mean effects

VTE Risk Difference (δ_V)	standardized effect on bleeding (δ_B)									
	-1.96	-1.64	-1.28	-0.84	0.00	0.84	1.28	1.64	1.96	
-1.96	0.979	0.955	0.909	0.813	0.512	0.203	0.103	0.050	0.024	
-1.64	0.974	0.949	0.896	0.793	0.482	0.185	0.089	0.043	0.021	
-1.28	0.966	0.938	0.875	0.765	0.450	0.160	0.076	0.036	0.016	
-0.84	0.951	0.913	0.842	0.717	0.394	0.132	0.059	0.027	0.012	
0.00	0.877	0.813	0.720	0.570	0.268	0.076	0.031	0.013	0.006	
0.84	0.690	0.612	0.503	0.363	0.144	0.033	0.012	0.005	0.002	
1.28	0.545	0.466	0.366	0.254	0.086	0.017	0.006	0.002	0.001	
1.64	0.411	0.345	0.262	0.170	0.054	0.010	0.003	0.001	0.000	
1.96	0.303	0.247	0.182	0.115	0.032	0.006	0.002	0.001	0.000	

Table 3: True mean difference between short and conventional duration therapy in different scales.

Scale	True mean difference on recurrent VTE or bleeding risks								
Standardized	-1.960	-1.645	-1.282	-0.842	0.000	0.842	1.282	1.645	1.960
¹ . S_{arr}	-0.049	-0.041	-0.032	-0.021	0.000	0.021	0.032	0.041	0.049
² . S_{arr}^V	-0.028	-0.024	-0.018	-0.012	0.000	0.012	0.018	0.024	0.028
³ . S_{arr}^B	-0.016	-0.014	-0.011	-0.007	0.000	0.007	0.011	0.014	0.016

¹. Assuming 10% event risk (standardized scale times 0.0251).

². Assuming 3% event risk (standardized scale times 0.0143).

³. Assuming 1% event risk (standardized scale times 0.0083).

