2.3 Analysis of tertiary and exploratory endpoints

2.3.1 Analysis of subgroups

If there are a sufficient number of events, the ARR for the primary and secondary efficacy and safety endpoints will be calculated separately within each level of the stratification variables.

3. APPENDIX: Bivariate decision criteria

The bivariate decision curve for the design of Kids-DOTT was derived from the 3 reference points in **Table 1** that were selected to capture a clinically meaningful balance between the potential benefits of symptomatic recurrent VTE risk reduction and the potential for increased clinically relevant bleeding risk. The bivariate decision curve of **Figure 1** is given by equation (1) below, which is based on the standard error of the ARR (S_{arr}) assuming a 10% risk for recurrent VTE and a 10% risk for clinically relevant bleeding. The bivariate NI bound is given by equation (2), which is the curve that is shifted by 1.96 standard errors to the northeast of the decision curve. If the bleeding and VTE risks differ from the original assumptions, then the revised decision curve shifted by 1.96 standard errors to the southwest of the NI bound (equation 3). The shifted decision curve (**Figure 2**, green line) is given by equation (3) using a 3% risk of symptomatic recurrent VTE ($\pi_V = 0.03$) and a 1% risk of clinically relevant bleeding ($\pi_B = 0.01$).

$$\text{ARR decision curve: } (ARR_V - 0.025)(ARR_B - 0.08) = 0.003 \quad (1)$$

$$\text{ARR null curve: } (ARR_V - 0.025 - 1.96S_{arr})(ARR_B - 0.08 - 1.96S_{arr}) = 0.003 \quad (2)$$

$$\text{Shifted decision curve: } (ARR_V - 0.025 - 1.96S_{arr} + 1.96S_{arr}^V)(ARR_B - 0.08 - 1.96S_{arr} + 1.96S_{arr}^B) = 0.003 \quad (3)$$

where $S_{arr} = \sqrt{0.1 \times 0.9 \times 2/285} = 0.0251$, $S_{arr}^V = \sqrt{\pi_V \times (1 - \pi_V) \times 2/285}$, and $S_{arr}^B = \sqrt{\pi_B \times (1 - \pi_B) \times 2/285}$, where π_V and π_B denote the 1-year risk of recurrent VTE and clinically relevant bleeding, respectively.

REFERENCES

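### The protocol's critical pair (+1% recurrent VTE, −5% bleeding) and its 82% power do not follow from the original design's decision curve, which needs −12% bleeding at +1% and gives about 36% power

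*Protocol*

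**What the plan says.** Protocol section IV.H gives one power statement and one critical pair. With 285 per group, "there is 82% power to conclude non-inferiority at an observed absolute increase in recurrent VTE of 1% (i.e., critical value of 1" (per cent; the sentence then gives an upper 95% limit below 6%), "with an observed absolute decrease in clinically significant bleeding of 5" (per cent). The paragraph before it in the same section makes the same pairing: an observed recurrence increase under 1%, and a hypothesised bleeding reduction of at least 5 points.

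The same section says that the original curve "is based on the original design assumption of a 10% risk for recurrent VTE and a 10% risk for clinically significant bleeding". The SAP defines that curve in two ways:

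- **Section 1.2.1 and Table 1** give three reference points (recurrence, bleeding): A (+1%, −12%), B (0, −4%) and C (−5%, +4%). The text describes A as "point A: -12% bleeding risk reduction".
- **Appendix equation (1)**, after its opening bracket, reads "ARR_V - 0.025)(ARR_B - 0.08) = 0.003".

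SAP Table 3 gives the standard error for this design: "Assuming 10% event risk (standardized scale times 0.0251". SAP Table 2 and the worked example in section 1.3.2 print 81.3% power at no recurrence difference and a bleeding reduction of 1.64 standard errors. Equation (3) moves the curve when the risks are 3% and 1%.

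**The concern.** The protocol pairs +1% recurrence with −5% bleeding. For the same design and sample size, the SAP pairs +1% with −12%. Both cannot lie on one curve.

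The 6% margin in section IV.H is justified by an expected bleeding benefit, so the exchange rate between the endpoints is what a reader needs to judge it. If the protocol figure is wrong, readers are shown less than half of the bleeding reduction that the original rule demands at +1%, with a power that the rule does not have.

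The sentence also attaches power to an observed difference. Power is defined at a true difference.

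**Working it through.** Write V and B for the differences in recurrent VTE and bleeding, shortened minus conventional.

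**Inputs.** n = 285 per group (Protocol IV.H). Risks of 10% and 10% (Protocol IV.H; SAP 1.1). Equation (1): (V − 0.025)(B − 0.08) = 0.003. Non-inferiority requires V < 0.025, B < 0.08 and a product above 0.003.

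**1. Which design the sentence describes.** SE = √(0.1 × 0.9 × 2/285) = 0.0251, and 1.96 × 0.0251 = 0.049. Then 0.01 + 0.049 = 0.059, which reproduces the upper limit just under 6%. The sentence is therefore about the 10%/10% design and equation (1).

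**2. The SAP's reference points lie on equation (1).**
- A: (−0.015)(−0.20) = 0.0030
- B: (−0.025)(−0.12) = 0.0030
- C: (−0.075)(−0.04) = 0.0030

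**3. The protocol's pair does not.** (0.01 − 0.025)(−0.05 − 0.08) = 0.00195 < 0.003. The rectangle rule in SAP 2.1.3 agrees: the upper corner is (+5.9%, −0.07%), and the equation (2) bound at that bleeding value is V = +5.1%, so the bound is not excluded.
- Bleeding needed at V = +1%: 0.08 − 0.003/0.015 = −0.12.
- Recurrence allowed at B = −5%: 0.025 − 0.003/0.13 = +0.0019, about +0.2 points.

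**4. Power under equation (1).** V and B are taken as bivariate normal, SE 0.0251 each, correlation 0, and the probability of the non-inferiority region is integrated numerically.

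| True V | True B | Power |
|---|---|---|
| +1% | −5% | 36% |
| 0 | −5% | 52% |
| 0 | −10% | 62% |
| 0 | −20% | 71% |
| −2.3% | −5% | 82% |

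At (+1, −5), correlations from −0.5 to +0.5 give 35% to 38%. Unpooled standard errors give 37%, and binomial simulation gives 37% with equation (1) and 38% with a Wald rectangle against equation (2). A 10-point bleeding reduction is the most possible if 10% is the conventional-arm risk; 20 points is the most possible if 10% is the pooled risk.

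**5. Other routes to 82%.** A recurrence-only test against 6% has 67% power at a true difference of 0 and 51% at +1. Bleeding superiority, 10% against 5%, has 62%. Neither gives 82%.

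**6. Probable source.** As labelled, SAP Table 2 differs from equation (1) by up to 0.49. With the recurrence and bleeding axes interchanged and a correlation of about −0.2, all 81 cells agree within 0.003. The cell behind the worked example prints 0.813; equation (1) gives about 0.49 there. The same interchange at (+1, −5) gives 80% at correlation 0, 81% at −0.2 and 82% at −0.3.

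**7. Updated curves, equation (3), risks 3% and 1%.** Recurrence allowed at B = −5%:
- 285 per arm: 0.0462 − 0.003/(0.1129 + 0.05) = +2.8 points
- 158 per arm (316 in total): 0.0366 − 0.003/(0.1073 + 0.05) = +1.8 points

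Neither gives +1. Nor can bleeding fall by 5 points from a 1% risk.

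**The case against.** **The 82% roughly agrees with the SAP.** This is fair as far as it goes. Reading Table 2 as printed near (+1, −5) gives about 79%, and the table shows 81.3% and 87.7% at no recurrence difference. But the worked example says that it uses equation (1), and equation (1) does not give those values as labelled. So the protocol probably inherited an error, and a correction to the protocol alone would create a new conflict with the SAP.

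**The 1% has a consistent one-endpoint reading.** It does: 1% plus 4.9 points is just under 6%. The fault lies in joining that one-endpoint critical value to a two-endpoint rule that sets a different boundary.

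**The original curve is no longer operative.** This stands, and it limits the point. A reader might infer that the trial would today call (+1%, −5%) a failure. The documents do not support that: both SAPs and protocol text on the updated design move the curve when risks are lower, and the 3%/1% curves accept the pair. Power at no difference on either endpoint is then about 91% (285 per arm) or 67% (158 per arm).

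**82% is not mathematically out of reach.** Also correct. At equal recurrence the limit as the bleeding reduction grows is Φ(0.025/0.0251) = 84%. But even an impossible 100-point reduction gives only 81.2%, so 82% is out of reach at any attainable reduction.

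**Timing.** The protocol reports primary endpoint data complete by January 2021 and the primary database locked in March 2021. No analysis depends on the sentence. It nevertheless stands in the current protocol, directly before the 420 and 316 targets, with nothing marking it as historical.

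**Conclusion.** The point holds for the original 10%/10% design with 285 per group. The stated pair falls short of equation (1) (0.00195 against 0.003). The bleeding reduction that goes with +1% is 12 points, and the recurrence difference that goes with −5% is +0.2 points. Power is 36% at true (+1, −5) and 52% at true (0, −5). Reaching 82% with a 5-point bleeding reduction needs recurrence to fall by about 2.3 points.

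The decision rule is internally consistent: equation (1) passes through all three of the SAP's reference points. The error is in the protocol's description of that rule and in the power attached to it. The interchanged axes in Table 2 are the likely explanation for the 82%, but the documents do not show how that figure was obtained.

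The power figures rest on a normal approximation. The documents give no correlation, and the range tried does not alter the conclusion. The exact intervals named in SAP 2.1.3 were not run. The critical pairs are arithmetic from the SAP's equations and do not depend on the correlation.

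**What to change.** Correct the protocol and the SAP together.

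- **Protocol IV.H:** label the sentence as the original 10%/10% design. Replace the critical pair with points on equation (1): (+1, −12), (0, −4) and (+0.2, −5). Reconcile the preceding paragraph, which pairs a rise under 1% with a 5-point bleeding reduction.
- **316-patient curve:** add pairs from equation (3) with 158 per arm. At 3% and 1% risks these are about (+0.9, 0), since 0.0366 − 0.003/0.1073 = 0.0087, and (+1, −0.5), since 0.1073 − 0.003/0.0266 = −0.005.
- **Power:** replace 82% with power at named true differences computed from the rule: 36% at (+1, −5) and 52% at (0, −5) for the original design. Drop the word observed from any power statement.
- **SAP 1.3.2:** correct the axes of Table 2 and the 81.3% worked example, which is about 49% under equation (1) as labelled.

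The cost is wording and one recalculated table. The decision rule, analysis and sample size do not change. The only downside is a less favourable stated power for the original design.
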